Through reinforcement of the mind-body connection, Tai Chi may be helpful in relieving chronic abdominal pain associated with IBS-C. The gentle moving meditation involved in Tai Chi practice may influence proper breathing and abdominal wall control in addition to massaging internal organs through movement.

Previous research has suggested that therapies engaging the mind-body connection may have promising effects on functional bowel disorders in general, and on IBS specifically. ^{18, 5} Some mind-body therapies, such as gut-focused hypnotherapy, have already gained approval as an effective treatment in reducing symptoms of IBS. ¹⁹ Similarly to already established mind-body therapies, Tai Chi may positively impact symptoms of IBS-C by changing sensory perception or even calming colonic motility. Tai Chi practice could lead to reduced abdominal distention and improved anxiety and depression scores.

II. Specific Aims

This is a single center pilot study. The purpose of the study is to evaluate the efficacy of Tai Chi practice in reducing symptoms of IBS. Patients who meet the Rome IV criteria for IBS-C and who meet the inclusion criteria will be offered participation in the study. We hypothesize that patients practicing Tai Chi will have reduced symptoms of IBS-C as measured through the Global Assessment of Relief, Irritable Bowel Syndrome Severity Scoring System (IBS-SSS), Irritable Bowel Syndrome Quality of Life (IBS-QOL), Visual Analogue Pain Scale, and abdominal distention. We also hypothesize that daily entries made through the GeoPain app will show a trend toward reduced pain intensity.

III. Subject Selection

This study aims to recruit 24 total subjects to be enrolled at one site, Massachusetts General Hospital. The 24 subjects that this study aims to recruit factors in a dropout rate of 15%, with a final sample size of 20 subjects.

INCLUSION/EXCLUSION CRITERIA:

Inclusion

- 1. Age 18 70 years
- 2. BMI \leq 35
- 3. Rome IV criteria for IBS-C
- 4. Continued IBS-C throughout run-in period
- 5. Compliant with reporting during run-in
- 6. Ability to follow verbal and written instructions
- 7. Ability to record daily patient reported outcomes via RedCap survey
- 8. Ability to use the GeoPain app on a smart phone
- 9. Ability to use Zoom as a platform for conducting study visits virtually
- 10. Ability to respond to 80% of the daily diaries
- 11. Ability to attend at least 7 out of 8 Tai Chi classes
- 12. Informed consent form signed by the subjects

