 - 1. Record whether study participant verbally states they are pregnant or not for women of child-bearing potential (If restrictions are lifted and study visits are being performed on site, perform urine pregnancy test on women of child-bearing potential) (performed by research staff)
 - m. Self-reported leg strength assessment

2. Run-In Period

After a screening visit in which patient eligibility will be determined through use of the Rome IV IBS-C criteria along with other inclusion and exclusion criteria as above, there will be a 2-week run-in period. The 2-week run-in period may occur up to 3 months before the trial start date to facilitate accumulation of enough patients for a 10-person class.

Prohibited Medications

During this time no use of contraindicated medication per exclusion criteria will be allowed.

a. Opiate and narcotic pain-relievers

Permitted Medications at Stable Doses

The following medications are permitted as long as the medication dose has been stable for 3 months prior to the run-in period:

- a. Laxatives (e.g. linaclotide, lubiprostone, bisacodyl, senna, MiraLAX)
- b. Prokinetic medications (e.g. domperidone, metoclopramide, erythromycin, prucalopride)
- c. Antidepressant medications (e.g. SSRIs, SNRIs, TCAs, trazodone, bupropion)
- d. Neuromodulators (e.g. gabapentin, pregabalin, buspirone)

- e. Aluminum/Magnesium
- f. Calcium-channel blockers (e.g. amlodipine, diltiazem, nifedipine, nicardipine)

During the run-in period, subjects will be asked to complete a daily REDCap diary entry, a daily GeoPain entry, as well as complete the Visual Analogue Pain Scale, and turn in a stool sample within 2 weeks before the start of the treatment period. A stool kit may be mailed to subjects' homes, which subjects will then mail completed back to the research site.

Rescue Medications

If a subject does not have any documented bowel movement for 5 consecutive days and is in need of a rescue treatment, they will be asked to please contact the study doctor or study coordinator immediately. The study doctor will recommend the following rescue treatments, as applicable, in the following order:

- a. Laxatives: either MiraLAX or Dulcolax
- b. Glycerin suppository
- c. Enema

Administration of the rescue treatment will be at the discretion of the investigator based on their assessment of the subject's symptoms; administration of rescue treatment will be monitored and recorded.

3. Treatment Period (Day 0 to 49)

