One day prior to the treatment period, subjects will again complete the Rome IV questionnaire confirming that inclusion and exclusion criteria continue to be satisfied.

Subjects will be asked to refrain from making any major lifestyle changes (e.g. starting a new diet or changing their exercise pattern outside of Tai Chi practice) during the study.

During the treatment period, subjects will meet via Zoom once per week for one-hour Tai Chi lessons with an experienced instructor. A member of the research staff will send the password-protected Zoom invitation link to the subject's preferred email address via Send Secure or regular email, depending on the subject's preference. Subjects will also be instructed to practice Tai Chi at home outside of the lessons using the instructions, handouts, and guidance from the instructor.

Subjects will be instructed to complete a daily REDCap diary entry and a daily GeoPain entry to record information about stool frequency and consistency, abdominal bloating, abdominal discomfort, and abdominal pain. Subjects will also use the REDCap diary to report rescue medication use and daily Tai Chi practice.

The lessons will occur on Days 0, 7, 14, 21, 28, 35, 42, and 49. The Tai Chi lessons will take place remotely via Zoom. Should restrictions be lifted and study visits be performed on site, lessons will take place in the Simches Research Center at [name].

On Days 0, 21, and 49 subjects will be phoned by a member of the research staff for

assessments prior to their regularly scheduled Tai Chi lesson. Assessments will include vitals (if the study is operating on site only), weight, height, waist circumference, leg strength, and questionnaires. Assessments will be completed with research staff over the phone or, if restrictions are lifted and study visits are conducted on site, at the Center for Neurointestinal Healthcare at [name], after which subjects will go to their regularly scheduled Tai Chi lesson at Simches. Participants will also complete a qualitative survey over the phone with a member of the study staff that will be audio recorded and later transcribed in order to gain a full, complete, qualitative understanding of the patient's perspective of the investigational treatment that was used.

4. Post-Treatment Period (Day 77)

Subjects will complete a REDCap diary entry regarding symptoms 28 days post-treatment, 4 weeks after the final study visit.

5. Schedule of Events

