Every session will include the following components: (1) Tai Chi warm ups with a strong emphasis on balance between strength and flexibility while reviewing Tai Chi principles; (2) Tai Chi breathing with self-massage (3) Tai Chi relaxation with meditation and visualizations (4) Tai Chi form which includes 10 moves from the Yang style Tai Chi (5) Tai Chi drills which are the Tai Chi individual postures practice (6) Tai Chi combination of movements and principles which are part of the Tai Chi philosophy. We will instruct patients to practice at least 30 minutes a day at home throughout the intervention period.

7. Data to be Collected and Timeline for Collection

- a. Primary endpoints
 - 1. IBS-SSS (pre-treatment, halfway point, and at conclusion of study)

b. Secondary endpoints

- 1. Likelihood of continuing treatment (5-point scale, end of study)
- 2. Treatment satisfaction (5-point scale, end of study)
- 3. Global Assessment of Relief and Visual Analogue Pain Scale (pre-treatment and each study visit)
- 4. Change of IBS-QOL, VSI, and HADS (pre-treatment, halfway point, and at conclusion of study)
- 5. For each BM: Bristol stool scale, stool frequency (CSBMs and SBMs; for each BM, during run-in and during study)
- 6. Waist circumference measurements (pre-treatment, halfway point, and at conclusion of study)
- 7. Daily: Bloating Scale, Abdominal Discomfort Scale, Constipation Severity Scale
- 8. Gastrointestinal Symptom Rating Scale-IBS version (GSRS-IBS), Irritable Bowel Syndrome-Behavioral Responses Questionnaire (IBS-BRQ), Fear of Food Questionnaire (FFQ) (pre treatment, study visit 2, and at conclusion of study)
- 9. Leg strength assessment patient (pre-treatment, halfway point, and at conclusion of study)
- 10. Instructor assessment as to confidence that patient has mastered technique (x1 at end of study, 5-point scale)
- 11. Client satisfaction questionnaire and qualitative survey (at conclusion of study)
- 12. Stool for metabolomics, and microbiome (pre-treatment and at conclusion of study)

8. Compliance

- a. Study coordinator will remind subjects of Tai Chi sessions and monitor completion of daily diaries, reports of home practice, and rescue medication use. Subject attendance will be monitored during each Zoom/in-person session by staff-completed attendance forms as well as class sign-in sheets. Number of missed sessions for each subject will be tracked.

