 Stool will be stored to check for metabalomics that may profile changes between the pre-treatment and treatment sample.
- 2. Microbiome Analysis
 Standard 16s rRNA sequencing for taxonomic identification and metagenomic profiling of the gut microbiome will be performed on stool samples to profile microbiome diversity and changes in microbiome between the pre-treatment and treatment sample.

VII. Biostatistical Analysis

- a.) Endpoint analyses
 - 1. Primary endpoint: IBS-SSS will be compared in a paired fashion for individual patients before and after the intervention using repeated measures t-test.
 - 2. Secondary endpoints: The secondary endpoints (as outlined in section V.a.6.b.) will be compared in a similar fashion.

b.) Power analysis

This is a single-center clinical exploratory pilot investigating the treatment of IBS-C using Tai Chi. As a pilot study, we hope to enroll 24 subjects with a final sample size of 20 subjects. The study will be conducted in two cycles of at least 10 subjects each to facilitate a full classroom size. Based on a previous pilot study involving Tai Chi as treatment for rheumatoid arthritis¹², 20 subjects appears to be a feasible number for detecting a trend toward outcomes that can be investigated in a future larger clinical trial.

VIII. Risks and Discomforts

a.) Tai Chi

Tai Chi is a relatively safe practice that is unlikely to cause injury if done with proper instruction. Caution should be exercised with conditions such as pregnancy, hernia, joint problems, and severe osteoporosis.

b.) Other Possible Risks

Other possible risks and side effects include skin irritation from inadvertently coming in contact with preservatives in the specimen collection materials, breach of confidentiality involving protected health information, and that information about taking part in a metabolic/microbiome study could influence insurance companies or employers regarding the patient's health. Study IDs will be utilized to minimize breaches of confidentiality. Filling out questionnaires could cause patients to feel uncomfortable.

IX. Potential Benefits

- a.) It is hypothesized that Tai Chi may be of benefit in patients with IBS-C. Potential benefits may include a decrease in self-reported abdominal pain/discomfort, straining, bloating, and constipation severity, as well as improved quality of life and symptoms severity.

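### Bristol stool scores after rescue are neither excluded nor flagged, so a participant whose constipation worsens can appear to improve in stool form (minor, secondary endpoint)

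*Combined protocol and SAP*

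**What the plan says.** Section V.b, item 7 (data to be collected), secondary endpoint 5, reads: "For each BM: Bristol stool scale, stool frequency (CSBMs and SBMs; for each BM, during run-in and during study". The Bristol score is attached to each movement. Frequency is expressed through two named classes, CSBMs and SBMs, and the document defines neither.

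The rescue paragraph in Section V.b, item 2 (Run-In Period) sets the condition: "If a subject does not have any documented bowel movement for 5 consecutive days and is in need of a rescue treatment". The first step is "Laxatives: either MiraLAX or Dulcolax", followed by a suppository and then an enema. Use is left to the investigator's judgement, and "administration of rescue treatment will be monitored and recorded". The paragraph stands under the run-in heading, but item 3 (Treatment Period) shows that rescue use is also captured during treatment: "Subjects will also use the REDCap diary to report rescue medication use and daily Tai Chi practice".

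Background laxatives are allowed at doses stable for 3 months before run-in: "Laxatives (e.g. linaclotide, lubiprostone, bisacodyl, senna, MiraLAX".

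Section IV.c assigns Tai Chi to every participant. Section VII.a gives a paired before/after t-test for IBS-SSS and says that the secondary endpoints "will be compared in a similar fashion". It does not mention stools passed after rescue.

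**The concern.** Rescue is tied to the symptom being measured: it becomes available when a participant has gone 5 days without a movement. The stools it induces therefore come from participants at their most constipated, and they are likely to be looser than unaided ones. If a higher Bristol type is read as improvement in a constipated population, each such stool pushes the participant's mean in the favourable direction for an unfavourable reason.

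In a before/after comparison this matters whenever rescue use differs between run-in and treatment. With no control arm, nothing shows how much of a shift in stool form comes from rescue. Stool form is a direct measure of constipation, and Section VII.b intends the pilot to detect trends worth pursuing in a larger trial.

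**Working it through.** **1. The plan's own figure.** The one design figure that can be recomputed is the recruitment target: "The 24 subjects that this study aims to recruit factors in a dropout rate of 15%, with a final sample size of 20 subjects". 20 / (1 − 0.15) = 23.5, rounded up to 24, which agrees. It has no bearing on the stool endpoint, except that step 5 uses the 20.

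**2. Inputs for the illustration.**
- From the documents: Bristol scored at each movement; rescue after 5 consecutive days without one; paired before/after analysis; one arm.
- Assumed: higher type means looser stool; each participant's scores are averaged over a period (the plan names no summary); the stool types and weekly counts below; a run-in mean of 1.5.

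**3. Stool form.** With s unaided stools of type 1 and r rescue-induced stools of type t per week, the mean over every movement is (s × 1 + r × t) / (s + r).

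| s | r | t | Mean, all movements | Mean, unaided only |
|---|---|---|---|---|
| 1 | 1 | 5 | (1 + 5) / 2 = 3.0 | 1.0 |
| 1 | 2 | 5 | (1 + 10) / 3 = 3.67 | 1.0 |
| 1 | 2 | 6 | (1 + 12) / 3 = 4.33 | 1.0 |
| 2 | 1 | 5 | (2 + 5) / 3 = 2.33 | 1.0 |
| 0 | 7/6 | 5 | 5.0 | none |

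The first row is compatible with the rescue condition: an unaided stool on day 1, none on days 2 to 6 (5 empty days), and a rescue-induced stool on day 7. Against a run-in mean of 1.5, that participant's change is 3.0 − 1.5 = +1.5 when every movement is used and 1.0 − 1.5 = −0.5 when only unaided movements are used. The sign reverses.

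**4. Sensitivity to the run-in mean.** For one unaided type-1 stool and one rescue stool of type t, the apparent change from a run-in mean m is positive when (1 + t) / 2 > m, that is, when t > 2m − 1. For m = 1.5 this needs t above 2; for m = 2.5, t above 4; for m = 3, t above 5. The lower the run-in mean, the more easily the reversal occurs.

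**5. Effect on the group mean.** If the first-row pattern held throughout treatment, each affected participant would move the mean change over 20 participants by (3.0 − 1.0) / 20 = 0.10 of a Bristol type; 2 such participants would move it by 0.20 and 5 by 0.50. If the pattern held in only some weeks, the effect would be smaller. The documents give no rescue rate, so no actual figure can be stated.

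**6. Frequency.** Take a participant with no unaided movements and one rescue-induced movement after every 5 empty days, a 6-day cycle. Counting all movements gives 7/6 = 1.17 per week. A spontaneous count that excludes rescue-induced movements gives 0. The plan names the restricted classes, so on the usual reading of SBM the worsening would show.

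**The case against.** Much of the opposing case is sound.

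- **Frequency is already restricted.** A reader might infer that worsening could also pass for better frequency, for instance from 1.0 unaided per week in run-in to 1.17 rescue-induced per week in treatment. The documents do not support that. Endpoint 5 names SBMs and CSBMs, not all movements, and nothing says that rescue-induced movements count. That example also fails on its own terms: one movement every 7 days leaves 6 empty days, so the participant would already meet the 5-day condition in run-in. What stands is narrower: neither term is tied to rescue use or to any interval after it.
- **The diary may already be adequate.** A reader might also infer that completeness of evacuation is not collected, because the diary description under Treatment Period omits it. That description is not exhaustive: it also omits the daily Constipation Severity Scale listed as secondary endpoint 7. The diary form is not in the documents, and naming CSBMs commits the study to collecting what they require. This is something to confirm, not a demonstrated gap.
- **Rescue use is recorded.** Staff and participants both record it, so post-rescue stools could be identified at analysis. That makes the problem easy to repair, but it does not supply the missing rule.
- **The stakes are limited.** This is one of twelve secondary items in an exploratory pilot, and the Constipation Severity Scale gives another place where worsening could appear. That is a fair reason to rank the point low.

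**Conclusion.** The point holds for stool form. As written, the Bristol endpoint takes in every movement, including those induced by rescue, and the analysis section does not separate them. In the assumed example a true change of −0.5 is recorded as +1.5. That rests on induced stools being looser, on a low run-in mean, and on more rescue in treatment than in run-in. If rescue is rare, or equally common in both periods, the distortion is small.

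For frequency, the only supported statement is that SBM and CSBM have no stated relation to rescue; a sign reversal in frequency does not follow from the plan. Nor do the documents show that any needed data will be lost. The primary endpoint, IBS-SSS, is unaffected. This is a minor matter, worth settling because it is cheap to do before analysis.

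**What to change.** In secondary endpoint 5, with a matching sentence in Section VII.a:

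1. Compute each participant's Bristol mean only from movements not preceded by rescue within a prespecified window. 24 hours is an example; the length is an analysis choice for the sponsor to fix in advance.
2. Define SBM and CSBM with the same window, applied identically in run-in and treatment.
3. State that unchanged, stable background laxative use does not disqualify a movement. MiraLAX appears both as a permitted background laxative and as a rescue option, so the record must show in which role it was taken.
4. Report rescue-use days per week by period beside the stool endpoints. A weekly rate is needed because run-in lasts 2 weeks and treatment runs from Day 0 to Day 49.
5. Confirm that the REDCap diary records the timing of rescue use and, for each movement, completeness of evacuation.

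The cost is one counting rule and one extra summary. Diary items need adding only if step 5 finds them absent. The downside is that a few movements drop out of the means and some participants may have few or no evaluable Bristol scores, as in the last row of the table. The rescue-day outcome makes those participants visible.

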- 31. Any other clinically significant disease interfering with the assessments according to the Investigator (e.g., disease requiring corrective treatment, potentially leading to study discontinuation)
- 32. Any relevant biochemical abnormality interfering with the assessments according to the Investigator
- 33. Inability to attend at least 7 out of the 8 Tai Chi classes
- 34. Inability to respond to 80% of the daily diaries

a.) Source of subjects and recruitment process

Subjects will be recruited from the MGH Gastroenterology Unit based on the enrollment criteria. GI physicians at MGH will be informed of the study and can refer patients if they are deemed appropriate for the study. Study staff will review subject's electronic medical records to confirm inclusion and exclusion criteria. Additionally, electronic medical records of potential subjects coming into the GI clinic for an appointment will be screened in order to identify eligible patients with IBS. When an eligible patient is identified, their provider will be contacted in order to confirm the patient's eligibility as well as to gain permission to contact the patient. The treating physician/investigator will first present the study to the subject during a clinic visit. If the subject is interested in the study, the subject will be approached by one of the licensed physician investigators listed on the protocol or the study coordinator to obtain consent. If treating physicians are approaching their own patients, consent will be obtained by a study coordinator to avoid any coercion. All patients will be explicitly told that their decision to enroll in the study will have no bearing on their current or future treatment and this statement will be mandated as part of the protocol.

Subjects may also be identified using the Research Patient Data Registry (RPDR) system. Electronic medical records of potential subjects will be reviewed to confirm inclusion and exclusion criteria. The patient's provider will be contacted to confirm the patient's eligibility as well as to gain permission to contact the patient. The recruitment letter by the PI and the patient's provider will be sent. Patients who agreed to direct contact (RODY YES) will receive a recruitment letter from the PI. If the patient does not contact the study coordinator within 1 week, they will be contacted by phone and/or email by the study coordinator. All subjects will undergo telephone prescreening by the study staff.

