Study Procedures	Screening	Run-In (Up	Treatment								Post- Treatment
Visit	Visit 1 (Up to 3 months prior to treatment)	to 3 months prior to Treatment)	Visit 2 (Day 0)	Visit 3 (Day 7)	Visit 4 (Day 14)	Visit 5 (Day 21)	Visit 6 (Day 28)	Visit 7 (Day 35)	Visit 8 (Day 42)	Visit 9 (Day 49)	4 Weeks Post- Treatment (Day 77)
Informed Consent	Х										
Inclusion/exclusion criteria	х										
Demographics, medical history, and medication history	Х										
Concurrent medical conditions and concomitant medications	х		х			х				х	х
Physical examination	X										
Vital signs	Х		Х			Х				Х	Х
Weight, height, waist circumference (a)	x		Х			Х				Х	×
Pregnancy test	Х										
Tai Chi Lessons			Х	Х	Х	Х	Х	Х	Х	Х	
Stool Sample	Х									Х	Х
Daily Diary		Х	Х	Х	Х	Х	Х	Х	Х	Х	Х
GeoPain Reporting		Х	Х	Х	Х	Х	Х	Х	Х	Х	Х
Global Assessment of Relief	х		х	х	х	х	х	х	Х	Х	Х
HADS	Х		Х			Х				Х	Х
VSI	Х		Х			Х				Х	Х
Visual Analogue Pain Scale	х		Х	Х	Х	х	х	х	Х	Х	Х

Rome IV Questionnaire	Χ							
IBS-SSS	Χ		Х		Х		Χ	Х
IBS-QOL	Х		Х		Х		Χ	Х
GSRS-IBS	Х		Х				Χ	Х
IBS-BRQ	Х		Х				Χ	Х
Fear of Food Questionnaire	Х		Х				Х	Х
Leg strength Assessment	Х		Х		Х		Х	Х
Treatment Satisfaction							Х	Х
Pre-treatment AE Assessment	Х	Х						
AE Assessment	Χ		Х		Х		Χ	Χ
Qualitative Post-Tx Survey							Х	
CSQ							Х	
Instructor Assessment							Х	Х

⁽a) Weight, height, and waist circumference are measured and BMI is calculated at initial screening visit only. Weight and waist circumference only is measured at subsequent visits.

6. Investigational Treatment to be Used

Subjects will practice Tai Chi via Zoom (if on site, at the Simches Research Center.) We will use a standardized Tai Chi protocol derived from previously tested trials ^{10,11,12,13}. The Tai Chi program will be based upon the classical Yang Tai Chi philosophy which includes 108 postures show to be a moderate intensity exercise.

In the first session, the Tai Chi instructor will explain the program, exercise theory, and procedures of Tai Chi. The patients will be provided with printed materials on the Tai Chi Mind-Body program including Tai Chi principles, practicing techniques, and safety precautions. Subjects will then begin Tai Chi practice under the instruction of the Tai Chi instructor. The Tai Chi instructor will have extensive experience (>20 years) conducting Tai Chi mind-body programs and will be following a Tai Chi protocol specifically designed for individuals with IBS-C.

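### The primary paired t-test on IBS-SSS names no analysis set, uses only people with both scores and leaves out Day 21, so exit related to response after Day 0 would bias the mean change in a direction that cannot be known in advance

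*Combined protocol and SAP*

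**What the plan says.** All references are to the combined protocol and SAP.

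- **Primary analysis (VII.a):** "IBS-SSS will be compared in a paired fashion for individual patients before and after the intervention using repeated measures t-test". Nothing is added about who is included or what happens when a score is missing.
- **Sample size (III):** the target of 24 "factors in a dropout rate of 15%, with a final sample size of 20 subjects". VII.b repeats 24 enrolled and 20 final.
- **Primary endpoint (V, Data to be Collected):** "IBS-SSS (pre-treatment, halfway point, and at conclusion of study". The treatment-period text gives the days: "On Days 0, 21, and 49 subjects will be phoned by a member of the research staff". The Schedule of Events marks IBS-SSS at screening and at Days 0, 21, 49 and 77.
- **Attendance:** exclusion criterion 33 is "Inability to attend at least 7 out of the 8 Tai Chi classes", a condition of entry. For people who have started, the Compliance section says only: "Number of missed sessions for each subject will be tracked".
- **Timing before treatment (V, Run-In Period):** "The 2-week run-in period may occur up to 3 months before the trial start date". The schedule allows the screening visit the same window.

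**The concern.** A before/after paired test needs two scores per person, so the default is a completer analysis that the plan never declares. Someone who gives a Day 0 and a Day 21 score and then leaves contributes nothing, although a score is in hand that says how that person was responding.

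Two choices also stay open until the scores are visible. One is whether a starter who attends fewer than seven lessons is counted. The other is which score is the before: screening or Day 0.

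IBS-SSS is the only primary endpoint, there is no control arm, and VII.b wants a trend to take into a larger trial. An error in the mean change would carry into that planning.

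**Working it through.** **1. The plan's own figure.** 20 / (1 - 0.15) = 23.5, rounded up to 24. This reproduces. If all the loss fell after Day 0, 24 starters and 20 analysed would leave 4/24 = 16.7% without a pair.

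**2. The bias identity.** With m the share lost,

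completer mean - all-starter mean = m × (completer mean change - leaver mean change).

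The sign depends only on who leaves. If leavers and completers change alike, the difference is zero.

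**3. Illustration.** The documents give no SD, correlation or exit pattern, so these are assumptions: SD 80 at each visit, correlation 0.6 between any two visits, true change -25 at Day 21 and -50 at Day 49, 24 starters, 15% lost after Day 21, and a logistic exit probability that depends on the Day 21 change. The SD of change is 80 × √(2 × 0.4) = 71.6, and the standard error with 20 people is 71.6 / √20 = 16.0. Simulated completer means against a true -50:

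| Exit odds ratio per SD of change | Poor responders leave | Improvers leave | 95% CI coverage |
|---|---|---|---|
| 1 (random) | -50.0 | -50.0 | 95% |
| about 1.6 | -52.6 | -47.4 | 95% |
| 2.7 | -54.7 | -45.3 | 94% |
| 20 | -58.2 | -41.8 | 92% |

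The errors are 2.6/50 = 5%, 4.7/50 = 9.4% and 8.2/50 = 16.4%. In standard errors they are 2.6/16 = 0.16, 4.7/16 = 0.29 and 8.2/16 = 0.51.

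A likelihood estimate from the three visits stays within 0.3 of -50 in every row. Where exit depends on response, its root mean squared error is about 2 to 7% lower than the completers'.

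If half the loss precedes Day 0 (22 starters, 2 lost), strong to very strong dependence gives completers of -53 to -56, or -47 to -45.

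**4. Where the three-visit model helps only partly** (same strong to very strong range):
- Poor responders all leave before Day 21: model -53 to -55, completers -55 to -58.
- Poor responders leave according to the unseen Day 49 change: model -57 to -63, completers about -59 to -67.
- Improvers leave according to the unseen Day 49 change: model -43 to -38, completers -41 to -33.

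**5. Assigning zero change to leavers.** The estimate is 0.85 × the completer mean.
- Random exit: 0.85 × (-50) = -42.5, which understates improvement.
- Poor responders leaving on the unseen Day 49 change: 0.85 × (-59.5) = -50.6, up to 0.85 × (-66.8) = -56.8. Leavers worsen on average in this case, so zero change overstates improvement.

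**6. The undated pair.** With no true change, 20 people and correlations of 0.4 to 0.8, the chance of a significant improvement (two-sided 5%) is about 2.5% for one fixed pair. It is about 4.6% for the better of two baselines against Day 49, and about 8.4% for the best of four pairs (either baseline, Day 49 or Day 77).

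**The case against.** This is an unpowered exploratory pilot with no decision threshold, and a final sample of 20 after dropout already implies completers. One sentence naming the set and the pair would close most of the gap, and a mixed model on about 20 people is partly a matter of preference. That limits the weight of the point. It does not remove it, because the Day 21 score is collected anyway and the t-test discards it.

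The size is also modest. The 10 to 16% figure needs odds ratios of 2.7 to 20 per SD of change, and even then the bias is about half a standard error or less. This stands. The interval used for the model in the simulation (t with completers minus 3 degrees of freedom) has not been shown to match a mixed model's small-sample method.

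A reader might infer four stronger things that the documents do not support:

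- **That the plan will exaggerate improvement.** Nothing predicts who leaves, so the error could go either way or be absent.
- **That four of 24 people will lack a Day 49 score.** The 15% is not dated. Two cycles of at least 10 people, with a run-in up to three months ahead, fit much of the loss falling before Day 0.
- **That participation ends 28 days after a person's last lesson, before Day 49 for early leavers.** That sentence (Adverse Events, item 3.b) concerns how long adverse events are collected, and it fits the normal course of Day 49 + 28 = Day 77. Home practice continues between lessons, so a last lesson need not be the last treatment. Nor do the documents say that someone who has stopped lessons still gets the Day 21 call.
- **That any of four pairs is equally open.** The endpoint list says conclusion of study, and section V places the Day 77 entry four weeks after the final study visit, so Day 49 is the natural after. The baseline is less clear: secondary endpoint 8 lists pre-treatment separately from visit 2, which is Day 0.

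**Conclusion.** The concern holds as a cheap improvement. The primary analysis is an undeclared completer analysis that omits a score already collected.

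If exit after Day 0 depends on response, the completers' mean change is off by about 5% under mild dependence and roughly 10 to 16% under strong to very strong dependence, in either direction, with interval coverage from about 95% down to 92%. These sizes rest on the assumed SD, correlation, true change and exit model. With exit that is random or before Day 0, the bias is nil.

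The three-visit estimate removes the bias only when exit depends on scores already seen. Otherwise it reduces it in part. Leaving the baseline open raises the chance of a spurious improvement from about 2.5% to 4 to 5%; about 8% is a worst case.

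The omission itself is certain from the text, and the magnitude is illustrative.

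**What to change.** In VII.a:

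1. Fix the pair in advance as Day 49 minus Day 0. Day 0 is the last score before the first lesson, while screening may be up to three months earlier.
2. Define the primary set as everyone with a Day 0 IBS-SSS who starts lesson 1, whatever their later attendance.
3. Estimate the contrast from a repeated-measures mixed model of Days 0, 21 and 49 (visit as a factor, unstructured covariance, small-sample degrees of freedom), with a 95% CI. Keep the completer paired t-test as a sensitivity analysis. With complete data the two estimates agree.
4. State that the planned Day 21 and Day 49 assessment calls are still offered to people who stop lessons, and clarify that the adverse-event sentence does not end outcome collection early.
5. Add a sensitivity analysis over a range of assumed changes for leavers, including zero change and worsening. Do not call zero change conservative.
6. Report losses before and after Day 0 separately, with reasons.

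**Cost:** a few sentences in VII.a and one clarified sentence under Adverse Events. The calls, and the payments at Days 0, 21 and 49, are already planned, and no new data item is needed. In the simulations the standard error ranged from about 2% smaller to about 7% larger, and the estimate may be less favourable. None of this turns a single-arm change into a treatment effect.
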